The PINNACLE Registry® is the largest outpatient cardiovascular clinical data registry in the world, with millions of patients drawn from thousands of sites around the US representing over 10,000 outpatient providers. The registry has a comprehensive goal of improved patient care. In addition to using the PINNACLE Registry®, non-PINNACLE sites within large health systems will be recruited and randomized into the intervention and usual care arms respectively.

[figure not shown]
The Specific Aims of this study will be:

- To evaluate ability of ACC Solution Sets and Patient Resources to improve initiation and titration
 of GDMT for eligible patients with HFrEF Left Ventricle Ejection Fraction (LVEF) ≤ 40%.
- To evaluate change in QOL between patients in the Intervention arm and the Usual Care arm.
- Examine relative change in GDMT among higher risk versus lower risk patients in the Intervention arm and Usual Care arm.

In this randomized registry trial, sites will be invited to participate in a 6-month study aimed at various processes of care in HFrEF. Sites would be informed that they might be asked to participate in an intensive intervention to improve GDMT prescription or in a study of QOL in HFrEF. Once a list of sites interested in participating is created, sites would be randomized into two arms: an intervention group and a usual care group.

AMERICAN

(**Figure 1**): This graphic shows both usual care and intervention arm tracts.

Study Population:

- Patients from practices participating in the PINNACLE Registry® (these include those that are
 part of integrated health systems, stand-alone, and other practice environments); as well as
 patients from other practices (these include those that are part of integrated health systems,
 stand-alone, and other practice environments) with pre-existing data interfaces with study
 partner HealthReveal.
- Patient cohorts will have the following **inclusion** criteria:
 - Age ≥18 years
 - Clinical diagnosis of HF with EF ≤40% documented within 1 year of enrollment
 - Receiving ≥1 oral medication for HF at study enrollment (including diuretics, ACEI/ARB/ARNI, beta-blockers, MRA, SGLT2i or thiazide diuretics.
- Patient cohorts will have the following **exclusion** criteria:
 - Current or anticipated participation in a clinical trial
 - Currently receiving comfort care or enrolled in hospice
 - Life expectancy <1 year
 - o History of or plan for heart transplantation or left ventricular assist device

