The recommended adjustment(s) will be conveyed using proprietary software from HealthReveal, with a suggested follow up plan. All reminders regarding dosing targets are based on the 2020 ACC Expert Consensus Decision Pathway for Optimization of Heart Failure Treatment.

Additionally, during visits at baseline, 3 months, and 6 months, the KCCQ-23 will be completed.

In the Usual Care arm, during visits at baseline, 3 months, and 6 months, the KCCQ-23 will be completed.

9. Risk/Benefit Assessment

As study procedures reflect optimized heart failure care via guideline recommendations supported by the clinical judgment of the managing physician, there is no envisioned procedural risk to patients through involvement in the study. No testing, time, risk, or procedures beyond those required for routine care will be imposed. The primary risk associated with this project is the potential for a breach of patient confidentiality. The ACCF has established a robust plan for ensuring appropriate and commercially reasonable physical, technical, and administrative safeguards are in place to mitigate such risks as described in the Data Management section of this protocol.

10. Costs to the Subject and Compensation

There are no costs or compensation to the patient for participation in the TRANSFORM-HFrEF study.

11. Data Analysis and Statistical Considerations

Primary endpoint; compared to usual care:

From baseline to 6 months change in average composite endpoint of target dose achievement for the main classes of drugs (RASi/beta blockers/MRA/SGLT2i) among eligible patients without documented contraindications or intolerance.

Goal doses will be based on the 2020 ACC Expert Consensus Decision Pathway for Optimization of Heart Failure Treatment (4).

To calculate this composite:

Numerator = receiving ARNI/ACEI/ARB at 50% or higher of target dose + receiving evidence-based beta blocker at 50% or higher of target dose + receiving MRA at 50% or higher of target dose + receiving SGLT2i at 50% or higher of target dose.

Denominator = eligible to receive ARNI/ACEI/ARB and no documented reason for not receiving higher dose, eligible to receive evidence-based beta blocker and no documented reason for not receiving higher dose, and eligible to receive MRA and no documented reason for not receiving higher dose, and eligible to receive SGLT2i and no documented reason for not receiving higher dose.

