Using this approach, each patient may contribute to the numerator or be in the denominator 1, 2, 3 or 4 times, depending on meeting criteria and if eligible in that domain. An advantage of this composite approach is that it allows for a holistic view of all classes of drugs considered and allows for assessment not only of up-titration but also down-titration as well.

Example of a patient without contraindications:

Therapy	Initial dose	≥50% target?	Final dose	≥50% target?
Sacubitril/valsartan	24/26 mg twice daily	No	96/104 mg twice daily	Yes
Carvedilol	6.25 mg twice daily	No	12.5 mg twice daily	Yes
Spironolactone	25 mg daily	Yes	25 mg daily	Yes
	Ratio = 0 + 0 + 1/1 +1 + 1= .33		Ratio = 1 + 1 + 1/1 + 1 + 1 = 1.0	
	Relative change = 66.7%			

Example of a patient with contraindication to spironolactone (previous hyperkalemia):

Therapy	Initial dose	≥50% target?	Final dose	≥50% target?
Sacubitril/valsartan	24/26 mg twice daily	No	49/51 mg twice daily	Yes
Carvedilol	6.25 mg twice daily	No	6.25 mg twice daily	No
	Ratio = 0 + 0 /1 +1= .000		Ratio = 1 + 0/1 + 1 = .50	
	Relative change = 50.0%			

Example of a patient with no contraindication to spironolactone but not receiving it:

Therapy	Initial dose	≥50% target?	Final dose	≥50% target?
Sacubitril/valsartan	24/26 mg twice daily	No	24/26 mg twice daily	No
Carvedilol	6.25 mg twice daily	No	6.25 mg twice daily	No
Spironolactone	0	No	25 mg daily	Yes
	Ratio = 0 + 0+ 0 /1 +1 + 1 = .000		Ratio = 0 + 0 +1/1 + 1 + 1 = .33	
	Relative change = 33.0%			

In the CHAMP-HF Registry, the score at baseline was 34.7%, while at 6 months it increased nominally to 36.3% ([name], *Confidential Personal Communication, January 2019*).

Secondary endpoints; compared to usual care:

- 1) Relative change in actual achieved doses of individual classes of pivotal therapies (RASi/beta blocker/ MRA/SGLT2i).
- 2) Relative change in achievement of target doses (yes/no) of pivotal therapies (RASi/beta blocker/MRA/SGLT2i).

Exploratory, compared to usual care:

- 3) Difference in patient-reported outcome/KCCQ-23 scores from baseline to 6 months.
- 4) Rate of \geq 25%, \geq 50%, \geq 75% and 100% improvement in scores.
- 5) Among those not taking an evidence-based beta blocker, % changed to evidence-based beta blocker during course of the study.
- 6) Change in % eligible taking RASi during course of the study.
- 7) Change in % eligible taking beta blocker during course of the study.

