- 8) Change in % eligible taking MRA during course of the study.
- 9) Change in % eligible taking SGLT2i during course of the study.
- 10) Relative improvement in GDMT composite score among subgroups of interest. This may include pre-specified analyses among patients the following characteristics:
 - a. Elderly patients (age ≥ 75 years)
 - b. New onset HF
 - c. Recently hospitalized patients
 - d. Those with LVEF <25%
 - e. Those with estimated glomerular filtration rate <30 mL/min/1.73m²
 - f. Baseline systolic blood pressure <100 mm/Hg
 - g. Absence of RASi at baseline
 - h. Absence of beta blocker at baseline
 - Patients with high baseline total medication burden (5 or more meds for all conditions)
 - j. Academic versus Private practice

Power calculations: The primary endpoint will compare central tendency in score changes between the two groups (6-month score - baseline score; this gives a range of score changes from -3 to +3). We will assume a 5% rate of score decreases, with rates for -3, -2 and -1 assumed equal between the two groups. To compare such changes a two-sided Wilcoxon ranksum test at a 0.05 significance level with 90% power will be employed. Assuming 5% of usual

care patients have an increase in score versus 10% of the intervention arm change by 1 point, a sample size of 2560 (1280 per arm) would be needed. Assuming a reasonable 20% loss to follow-up and/or missingness in this registry analysis, this makes a total of 3072 (1536 per arm). This not only provides power for the primary endpoint, but also for the secondary and exploratory endpoints, including change in QOL metrics.

12. Data and Safety Monitoring

This is an observational study comparing the effectiveness of two standards of care based on secondary use of data collected in the conduct of care and patient reported outcomes. The purpose of this study is not to gather data with regards to the safety profile and/or effectiveness of specific drugs. This study does not proscribe which treatment patients will receive. There is no Data Safety Monitoring Board for this study.

Adverse events (should they occur) will be captured at the clinical site level. Patients reporting adverse events will address these with their providing physician.

13. Data Storage and Confidentiality

Please refer to the Data Management section for details regarding how data captured in this study is stored and how the confidentiality of such data is maintained.

References

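### The primary test compares unadjusted change in a bounded score between site-randomised arms, so a chance baseline gap carries into the effect estimate

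*Protocol*

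**What the plan says.** Section 11 defines the primary endpoint as "From baseline to 6 months change in average composite endpoint of target dose achievement for the main classes of drugs", compared with usual care. The composite is a ratio: classes at 50% or more of target dose, over classes for which the patient is eligible.

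The power paragraph of the same section describes the comparison as one of "score changes between the two groups (6-month score - baseline score; this gives a range of score changes from -3 to +3". It then names the test: "To compare such changes a two-sided Wilcoxon ranksum test at a 0.05 significance level with 90% power will be employed". The planning assumptions are "We will assume a 5% rate of score decreases, with rates for -3, -2 and -1 assumed equal between the two groups", increases in 5% of usual care patients, and for the other arm "care patients have an increase in score versus 10% of the intervention arm change by 1 point". The result is "a sample size of 2560 (1280 per arm) would be needed".

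The only empirical anchor for the score is a registry figure: "In the CHAMP-HF Registry, the score at baseline was 34.7%, while at 6 months it increased nominally to 36.3"%.

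On allocation, section 3 says that "sites would be randomized into two arms: an intervention group and a usual care group". It gives no number of sites and describes no stratification or matching on baseline treatment. The protocol does not name the baseline score as a covariate or stratifier for the primary comparison. Absence of RASi or of beta blocker at baseline appears only among the exploratory subgroups.

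**The concern.** The score has a floor and a ceiling. A patient with no class at target can only stay or rise, and a patient with every eligible class at target can only stay or fall. Expected change therefore depends on the starting score even if the intervention does nothing. Subtracting the baseline does not remove that dependence; conditioning on it does.

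The arm that happens to start lower will tend to show the larger change. Randomising practices rather than patients makes a noticeable difference in starting score more likely. The rank-sum test on raw change has no means of allowing for it. At stake are how far the single estimate the trial will produce can be trusted, given the baseline gap it happens to have, and some precision.

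**Working it through.** **Inputs from section 11.** Baseline 34.7%; decreases 5% in both arms; increases 5% against 10%; 1280 per arm.

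**Assumptions (not in the protocol).** Each class is on or off target independently; transition rates are the same in every class and at every site; three eligible classes (the stated range of -3 to +3 fits three, although four are named); intra-site correlation (ICC) of the baseline score 0.05 to 0.10; 10 to 50 sites per arm.

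**1. The plan's own figure.** Take down/none/up as 5/90/5 against 5/85/10.
- P(higher) + ½P(tie) = 0.1375 + 0.38625 = 0.52375.
- Tie factor = 1 - (0.05³ + 0.875³ + 0.075³) = 0.3295.
- N = (1.960 + 1.282)² × 0.3295 / (3 × 0.02375²) ≈ 2046.
- 2046/0.8 = 2558, so the stated 2560 is matched only if 20% loss is already inside it. Taken literally, 1280 evaluable patients per arm give about 95% power. That is a separate matter; it matters here only as the starting power in step 4.

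**2. Slope of change on baseline.**
- Rate up per class not at target: u = 0.05/(3 × 0.653) = 0.0255.
- Rate down per class at target: d = 0.05/(3 × 0.347) = 0.0480.
- For a patient with baseline share b, expected change = u(1 - b) - d·b, so the slope is -(u + d) = -0.0736.

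**3. Shift from a baseline gap.**
- A 5-point gap moves the difference in change by 5 × 0.0736 = 0.37 points.
- The planned effect on the ratio scale is 5%/3 = 1.67 points, and 0.37/1.67 = 22%.
- With four classes it is 0.28 of 1.25, again 22%, because the number of classes cancels.

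**4. What that does to the test, given the gap.** Simulated trials with 1280 independent patients per arm and the gap imposed. The ranges cover repeated runs of the three-class model, with four-class results where available.

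| Baseline gap (points) | Rank-sum rejection, no true effect | Baseline-adjusted regression |
|---|---|---|
| 0 | 4–6% | 4–6% |
| 2.5 | 7–8% | 4–6% |
| 5 | 12–16% | 4–6% |
| 7.5 | 25–26% | 4–6% |

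With the planned effect present and the intervention arm starting 5 points higher, rank-sum power fell from 93–95% to 72–75%. The adjusted model stayed at about 95% or above.

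**5. How large a gap can chance produce?** Patient variance of the baseline share = 0.347 × 0.653/3 = 0.0755. With k sites per arm and m = 1280/k patients per site, SD of the gap = √[2 × 0.0755 × (ICC + (1 - ICC)/m)/k].

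| Setting | SD (points) | 95% range |
|---|---|---|
| Independent patients: √(2 × 0.0755/1280) | 1.1 | ±2.1 |
| ICC 0.05, 10 sites per arm | 2.9 | ±5.8 |
| ICC 0.05, 20 sites | 2.2 | ±4.3 |
| ICC 0.05, 50 sites | 1.6 | ±3.2 |
| ICC 0.10, 10 sites | 4.0 | ±7.9 |
| ICC 0.10, 20 sites | 2.9 | ±5.8 |
| ICC 0.10, 50 sites | 2.0 | ±4.0 |

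A 5-point gap lies inside the range for 10 sites per arm at either ICC and for 20 at ICC 0.10, but not for 50.

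**6. Error rate when the gap is left to chance.** Null simulations with the gap arising from site randomisation:
- Independent patients: the rank-sum test rejects in 4.9%.
- ICC 0.05 with 50, 20 and 10 sites per arm: 5.6%, 5.9% and 9.4%.
- ICC 0.10, same site numbers: 7.0%, 8.3% and 11.3%.
- An unadjusted t-test on site-mean change: 5.0–5.7% in every setting.

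**7. Precision.**
- With independent patients, adjustment removes 0.0736² × 0.0755 = 0.00041 of a change variance of about 0.10/9 = 0.0111, or about 4%.
- With site randomisation the removable part is 0.0736² × (gap SD)². At ICC 0.10 and 10 sites this is 0.0736² × 0.0402² = 8.8 × 10⁻⁶, against a remainder of 2 × (0.0111 - 0.0004)/1280 = 1.67 × 10⁻⁵, a cut of about 34%.
- At ICC 0.05 and 50 sites the same arithmetic gives about 8%. Simulation over the same settings gave about 9–36%.

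**The case against.** The strongest reply has four parts.

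- **Unadjusted change is valid under randomisation.** This stands. Averaged over possible allocations the shift cancels, so the contrast is not biased. The protocol also gives a reason for using change: it captures down-titration as well as up-titration.
- **The inflated rejection rates belong to clustering.** A reader might infer from the table in step 4 that the test's type I error is 12–26%, or that the problem exists regardless of within-site correlation. Neither follows. Those rates hold a chosen gap fixed. With independent patients a 5-point gap is about 4.6 SDs (5/1.1) and would not arise by chance. Once a site-aware analysis is used, the unconditional error rate returns to about 5% without baseline adjustment. What is left is conditional distortion and lost precision.
- **Covariates are usually left to the SAP.** Partly fair: the test is named in the power paragraph, and an unseen SAP might add an adjusted model. But the protocol does not leave the method open. It says which test will be used on which variable, and a different primary analysis would need that text to change.
- **The size rests on assumed inputs.** Correct. The protocol gives no number of sites, ICC or score SD, and the on/off model with equal rates everywhere is a simplification. With many sites the effect is small: at ICC 0.05 and 50 sites per arm, the SD of the shift is 1.6 × 0.0736 = 0.12 points, 7% of the planned effect.

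Nor should availability of the baseline be overstated. It is present by construction for every patient with a change score, not necessarily for everyone enrolled; the plan allows 20% loss or missingness.

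**Conclusion.** The point holds in a limited form. As written, the primary analysis leaves the estimate exposed to whatever baseline gap the one site randomisation produces. The exposure is about 0.074 points per point of gap, or 22% of the planned difference for a 5-point gap. That figure depends on the assumed on/off model and equal transition rates, not on the number of classes. Whether such a gap is realistic depends on the number of sites and the ICC, neither of which is stated; it is plausible at 10 to 20 sites per arm and unlikely at 50. The documents do not support a claim of bias over repeated randomisation, or of an error-rate problem beyond the one caused by ignoring sites. Adjustment protects against the imbalance that occurs and, under the assumed site settings, reduces the variance of the effect estimate by roughly 8–36%. It is a free improvement rather than a correction of an invalid test.

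**What to change.** In section 11, replace the rank-sum test on change with a site-aware comparison of the 6-month composite score between arms, with the baseline composite score and the number of eligible classes as covariates. Report the unadjusted change by arm descriptively. If a rank test is preferred, stratify it by baseline score (van Elteren) and account for site. Make this change together with the handling of clustering, since both concern the same sentence of the protocol.

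The cost is a sentence or two in the protocol, mirrored in the SAP. No new data are needed and no patient is lost from the analysis, because each change score already requires its baseline value.

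### Section 11 scores the primary endpoint in three incompatible ways: a four-class ratio, a three-class ratio and a three-class count

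*Protocol*

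**What the plan says.** All of this is in the protocol, mostly in section 11 (Data Analysis and Statistical Considerations).

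- **Definition.** The endpoint is the change from baseline to 6 months in "target dose achievement for the main classes of drugs (RASi/beta blockers/MRA/SGLT2i) among eligible patients without documented contraindications or intolerance". The numerator includes "receiving SGLT2i at 50% or higher of target dose" and the denominator includes "eligible to receive SGLT2i and no documented reason for not receiving higher dose". The text adds that "each patient may contribute to the numerator or be in the denominator 1, 2, 3 or 4 times". This is a ratio over up to four classes.
- **Worked examples.** The first is headed "Example of a patient without contraindications". It lists a RASi, a beta blocker and an MRA, and its baseline line reads "Ratio = 0 + 0 + 1/1 +1 + 1= .33". The second patient has a contraindication to spironolactone and a denominator of 2. The third is eligible for spironolactone, does not take it at baseline, and has a denominator of 3. No example has an SGLT2i row.
- **Power paragraph.** The change is the 6-month score minus the baseline score, and "this gives a range of score changes from -3 to +3". Decreases are placed at -3, -2 and -1. The effect is a one-point increase in 10% of the intervention arm, against increases in 5% of usual care.
- **Benchmark.** The score is put in context with a registry: "In the CHAMP-HF Registry, the score at baseline was 34.7" per cent, then 36.3% at 6 months. Section 2 says that this registry reported no SGLT2i use.

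**The concern.** These passages describe one primary score and do not agree on it. The definition and the examples agree that it is a ratio but differ on the number of classes. The power paragraph differs from the definition on both. No passage reconciles them.

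A patient's score, and sometimes the direction of change, depends on the version used. Take a patient eligible for all four classes whose only change is starting an SGLT2i at or above half the target dose. That patient gains 25 points under the definition and nothing under the scheme of the examples. If another class falls below threshold at the same time, the change is zero under the definition and a decrease under the examples. Ratio and count also rank patients differently: one class gained of two eligible (+.50) and one of four (+.25) are tied as counts but not as ratios. If the choice is left open until data are seen, the primary endpoint is in effect chosen afterwards.

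**Working it through.** **1. Which score gives -3 to +3?** With k eligible classes, each met or not met, a count changes by -k to +k and a ratio by -k/k to +k/k.

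| Score | Range of change | One class gained |
|---|---|---|
| Count, 3 classes | -3 to +3 | 1 |
| Count, 4 classes | -4 to +4 | 1 |
| Ratio, 1 to 4 classes | -1 to +1 | 1, .50, .33 or .25 |

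Only the three-class count reproduces the stated range. On the ratio a one-point increase means going from 0 to 1.0, the maximum.

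**2. The examples under the written definition.**

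- Example 1, SGLT2i eligible and not received: (0+0+1+0)/4 = .25, then (1+1+1+0)/4 = .75, a change of +50 points. The protocol shows .33 to 1.0, +66.7. If SGLT2i were received at both times, the scores would be 2/4 and 4/4, again +50. With four classes, changes come in steps of 25 points, so 66.7 cannot occur.
- Example 2, *if* SGLT2i is eligible and not received: 0/3 to 1/3, +33.3 instead of +50.0.
- Example 3, on the same assumption: 0/4 to 1/4, +25 instead of +33.

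**3. Does the range affect the sample size?** The tie-corrected Wilcoxon formula per arm is n = (z₀.₉₇₅ + z₀.₉₀)² × (1 − Σp̄³) / [6 (P − ½)²]. Here p̄ is the mean category probability over the arms, and P is the chance that an intervention patient outscores a usual-care patient, ties counting half. Patients are treated as independent.

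- Stated rates: the 5% of decreases split over three levels, then 90% no change and 5% up by one (usual care) against 85% and 10% (intervention).
- P − ½ = .05 × (.90 + .05)/2 = .02375.
- 1 − Σp̄³ = 1 − (.875³ + .075³ + 3 × .01667³) = .3296.
- n = 10.507 × .3296 / (6 × .02375²) = about 1023 per arm, 2047 in total.

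This does not reproduce the protocol's 2560. At 1280 per arm the stated rates give about 95% power. With the decreases split over four levels (1.25% each), the total is again about 2047. A simulation with assumed eligibility mixes (10/30/60% eligible for 1/2/3 classes; 5/15/35/45% for 1/2/3/4) gave 94% to 96% power at 1280 per arm for count and ratio alike.

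**4. Could SGLT2i starts change the power?** The protocol gives no SGLT2i start rate, so every rate below is an assumption, with 5% decreases in both arms.

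| Increases, usual care vs intervention | Total N for 90% power | Power at 2560 |
|---|---|---|
| 10% vs 15% | about 2710 | 88% |
| 20% vs 25% | about 3772 | 76% |
| 10% vs 20% | about 752 | over 99.9% |
| 20% vs 30% | about 996 | over 99.9% |

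If starts raise both arms equally, power falls. If the intervention also widens the difference, power rises.

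**The case against.** The strongest reply is that the written definition is itself an operational specification. It names SGLT2i in the numerator and the denominator, allows up to four contributions, and is matched by SGLT2i in the secondary and exploratory endpoints. A programmer who follows it will not lose the class, and examples only illustrate. That stands against any claim that SGLT2i will be dropped from the endpoint. It does not remove the conflict, because the same section illustrates and powers a different score.

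A second reply is that examples 2 and 3 speak only of spironolactone and never say that the patient is eligible for SGLT2i. That also stands: those two are incomplete, and wrong only on an assumption. Example 1 is different. A patient without contraindications should have all four classes in the denominator, unless eligibility for SGLT2i is narrower than having no contraindication, which the protocol does not say. Nor can the class be left out because it is not being taken: example 3 gives an eligible, untaken drug its own row, a zero and a place in the denominator.

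A third reply is that a rank test depends on category probabilities, not labels, so the wrong range does no numerical harm to the sample size. The check above confirms this.

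**Conclusion.** The contradiction is real and concerns the primary endpoint. Section 11 contains a four-class ratio, a three-class ratio and a three-class count. For the one example that conflicts without further assumption, the change is +50 points under the definition (SGLT2i eligible and not received) against +66.7 as printed. The range and the one-point effect in the power paragraph do not belong to the defined score.

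A reader might go further in two ways that the document does not support. One is that the range makes the sample size wrong; correcting it leaves the total at about 2047 at the stated rates. The other is that the trial loses power because the 5% and 10% rates leave out SGLT2i starts. The protocol does not say how those rates were derived or what uptake to expect, and plausible assumptions move power in either direction, so no power loss is claimed. Likewise, the CHAMP-HF percentages are context and not stated as power inputs. They cannot reflect uptake of the fourth class, since the registry reported no SGLT2i use.

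**What to change.** - State once which score is analysed: four classes, as a patient-level ratio over the classes for which the patient is eligible, in line with the written definition.
- Add the SGLT2i term to example 1. State SGLT2i eligibility in examples 2 and 3, and recompute all three.
- Replace the range by -1 to +1 and express the one-point effect on that scale. If a count is really intended, change the definition and use -4 to +4.
- Note beside the 34.7% and 36.3% figures that the registry reported no SGLT2i use.
- Confirm whether the 5% and 10% increase rates apply to the four-class score. If they do not, justify new ones and rerun the power calculation.

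The cost is protocol wording and, at most, one rerun of the power calculation. It should be settled before anyone sees outcome data by arm.

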To evaluate contemporary status of GDMT delivery for HFrEF, the recent Change the Management of Patients with Heart Failure (CHAMP-HF) registry included 3518 patients from 150 primary care and cardiology practices (1,2). The mean age of this cohort was 66 ± 13 years, 29% were female, and mean EF was $29 \pm 8\%$, thus representing a very characteristic population of patients with HFrEF.

In CHAMP-HF, the investigators found 27%, 33%, and 67% of eligible patients were not prescribed angiotensin converting enzyme inhibitor (ACEI)/angiotensin II receptor blocker (ARB)/angiotensin receptor/neprilysin inhibitor (ARNI), beta-blocker, and mineralocorticoid receptor antagonist (MRA) therapy, respectively. Furthermore, when medications were prescribed, few patients were receiving target doses of ACEI/ARB (17%), ARNI (14%), and beta-blocker (28%); most patients were receiving target doses of MRA therapy (77%). Most notably, among patients eligible for all classes of medication, only 1% were simultaneously receiving target doses of renin-angiotensin system inhibitors (RASi; ACE/ARB/ARNI), beta-blocker, and MRA. Remarkably, little improvement in GDMT was noted over a 6 to 12-month period and (importantly) no use of the newest HFrEF GDMT, sodium glucose cotransporter-2 inhibitors (SGLT2i) was reported.

In analyses to better understand the reasons for these treatment gaps, the authors found no explanation based on blood pressure or heart rate limitation, suggesting clinician entropy and/or lack of understanding/confidence regarding guideline-directed targets might have been present. In adjusted models, older age, lower blood pressure, more severe functional class, renal insufficiency, and recent HF hospitalization generally favored lower medication utilization or dose, indicating as in prior studies a "risk-treatment mismatch" wherein the highest risk patients received the least aggressive care. Closure of this mismatch would be expected to have substantial impact on outcomes, given the higher baseline risk of such patients.

Understanding reason(s) for pervasive gaps in GDMT is important to make strides to improve prescription of life-saving therapies to those patients affected by HFrEF. The reasons for inadequate GDMT may include clinician-based factors, while others may be related to patient factors:

Clinician factors: Within the context of the 20-minute visit, clinicians caring for those patients

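### Sites are randomised, but the 2560/3072 sample size and its 90% power are presented as a patient-level Wilcoxon calculation with no clustering inputs, so the 90% is unsupported for this design

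*Protocol*

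**What the plan says.** Protocol section 3 (Design and Procedures) makes the site the unit of allocation: "Once a list of sites interested in participating is created, sites would be randomized into two arms: an intervention group and a usual care group". Practices outside the registry are treated the same way: "non-PINNACLE sites within large health systems will be recruited and randomized into the intervention and usual care arms respectively". The dashboard and clinician tools are supplied to the site.

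The power paragraph in section 11 is written entirely at patient level. The outcome is each patient's change ("6-month score - baseline score; this gives a range of score changes from -3 to +3"). The rates are rates among patients: "We will assume a 5% rate of score decreases, with rates for -3, -2 and -1 assumed equal between the two groups", with an increase in 5% of usual care patients and 10% of intervention patients. The test and target are stated as "To compare such changes a two-sided Wilcoxon ranksum test at a 0.05 significance level with 90% power will be employed", and the conclusion is that "a sample size of 2560 (1280 per arm) would be needed". One inflation follows, from 2560 to 3072, and it is attributed to loss to follow-up or missing data at 20%. No number of sites, site size, ICC or design effect appears anywhere in the protocol.

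**The concern.** Patients at one site share clinicians and, in the intervention arm, one dashboard. The outcome is prescribing, and the protocol's own background attributes treatment gaps partly to clinician behaviour. Some correlation of score changes within site is therefore to be expected. With site allocation, that correlation lowers the power of any valid between-arm comparison, and the number and size of sites then matter as much as the number of patients.

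If the printed power is too high, a null result could be read as evidence that the tools do not work when the trial was simply too small in sites. An analysis plan that handles clustering correctly would protect the error rate. It would not make this sample size or this 90% right, because both are fixed in the protocol and the number of sites is settled at recruitment.

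**Working it through.** **Inputs from section 11.** Two-sided α = 0.05; power 90%; decreases 5% in both arms, read as a total; increases 5% versus 10%, all placed at +1; 1280 per arm before loss and 1536 after. Evaluable with 20% loss: 1536 × 0.80 ≈ 1229 per arm, 2458 in total.

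**1. Trying to reproduce 2560 with independent patients.** Usual care is 5% down, 90% unchanged, 5% up; intervention is 5%, 85%, 10%.

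- P = P(Y > X) + ½P(Y = X) = (0.10 × 0.95 + 0.85 × 0.05) + ½(0.05 × 0.05 + 0.85 × 0.90 + 0.10 × 0.05) = 0.1375 + 0.38625 = 0.52375.
- Tie term, from the average proportions with the 5% split equally over −1, −2 and −3: Σp̄³ = 0.875³ + 0.075³ + 3 × 0.0167³ ≈ 0.6704.
- Noether's formula with ties: N = (1.960 + 1.282)² × (1 − 0.6704) / (3 × 0.02375²) ≈ 2047 in total.

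The stated 2560 is not reproduced. Leaving the 5% decrease unsplit changes almost nothing (about 2046).

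**2. Independent-patient power at the printed sizes.** With n per arm, power = Φ{[(P − 0.5)√n − 1.960√(2V₀)] / √(V₁ + V₂)}, where V₀ = (1 − Σp̄³)/12 = 0.02747, V₁ = 0.02141 and V₂ = 0.03329.

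- n = 1280: 95.2%.
- n = 1229: (0.8325 − 0.4594)/0.2339 = 1.595, so 94.5%.

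**3. How much clustering the surplus would cover.** 2458/2047 = 1.20 at the evaluable number, or 2560/2047 = 1.25 before loss. With design effect DE = 1 + (m − 1) × ICC, a DE of 1.20 is reached at ICC = 0.20/18 ≈ 0.011 for m = 19 and 0.20/19 ≈ 0.011 for m = 20.

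**4. Illustrative power for the site-randomised design.** Replace n = 1229 by 1229/DE. The protocol gives neither m nor ICC, so both are assumed. The middle row borrows a site size from the CHAMP-HF registry cited in section 2 ("registry included 3518 patients from 150 primary care and cardiology practices"): 3518/150 = 23.5 per practice, × 0.80 = 18.8 evaluable.

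| Evaluable per site | ICC 0.01 | 0.02 | 0.05 | 0.10 |
|---|---|---|---|---|
| 10 | 93% | 91% | 84% | 73% |
| about 19 | 91% | 86% | 73% | 57% |
| 50 | 83% | 71% | 48% | 31% |

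Example: m = 18.8 and ICC = 0.05 give DE = 1.89, an effective 650 per arm, and power 73%. A simulation of 65 sites per arm with 19 patients each, analysed by a site-level t test on mean ranks, gave 94%, 85%, 73% and 57% at realised ICC of 0, 0.024, 0.049 and 0.098.

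**5. Sensitivity to the decrease rate.** If 5% applies at each of −1, −2 and −3, then P = 0.52125 and Σp̄³ = 0.4663. The requirement becomes 10.507 × 0.5337 / (3 × 0.02125²) ≈ 4140 patients, and power at 1229 per arm is about 70.5% before any clustering.

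**The case against.** The strongest reply is that 2560 exceeds what the printed rates require, so some clustering is already affordable. That is true as arithmetic: power stays at or above 90% at ICC 0.01 with 19 per site and at ICC 0.02 with 10 per site. But the protocol does not describe the excess as a clustering allowance, and it covers a design effect of only 1.20 to 1.25. It might even be the loss allowance entered once already, since 2047/0.8 ≈ 2559. That too is only a guess, because the protocol presents 2560 as the figure before loss.

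The same arithmetic rules out a stronger statement. A reader might infer that 90% is the power 2560 patients would have if individually randomised. The printed rates give 95% for that trial, so the origin of 2560 is unknown. All that can be said is that it is presented as a patient-level figure.

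A reader might also infer that the trial is underpowered, or that it will fill from a few large health systems. The documents support neither. ICC and site size are absent, the 19 per site comes from an external registry and not from this trial, and health-system sites are recruited in addition to PINNACLE practices.

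Finally, the power loss appears once the analysis respects site allocation. Applied to patients as if independent, the rank-sum test would instead inflate the type I error. That is a separate consequence of the same mismatch.

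**Conclusion.** The point stands in this form: allocation is by site, the sample size is justified as if patients were independent, and the 90% power is unsupported for the design. That mismatch is explicit and rests on no assumption.

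The size of any shortfall is conditional. With decreases totalling 5% and 1229 evaluable per arm, power in the grid runs from about 93% (10 per site, ICC 0.01) to about 31% (50 per site, ICC 0.10). It falls below 90% once the ICC passes about 0.011 at 19 to 20 per site. The grid uses a simple design effect, equal site sizes and a normal approximation; unequal sites or few sites would lower these figures. It also credits the trial with the unexplained surplus over 2047. Under the other reading of the decrease rate, power is about 70.5% even with no clustering.

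**What to change.** Revise the power paragraph in section 11; the target of 3072 can stay.

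- State the planned number of sites per arm and the expected evaluable patients per site.
- Replace the flat 90% with power for the site-randomised design over a printed grid, for example ICC 0.01, 0.02, 0.05 and 0.10 at several site sizes, with degrees of freedom based on the number of sites.
- Show how 2560 follows from the inputs, and say whether decreases total 5% or are 5% at each level.
- Estimate the ICC of the 6-month change from existing PINNACLE data where possible. For non-PINNACLE sites it remains an assumption and should be labelled so.

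The cost is one rewritten paragraph and a short calculation, with no extra patients. The downside is a less favourable stated power. If the grid looks poor, a minimum number of sites or a cap on patients per site is an option. It could mean opening more sites and is not needed to correct the statement.
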